## 5.2 Exclusion Criteria

Patients who meet any of the following criteria will be excluded from registration:

### *Cancer-Specific Exclusion Criteria*

- Spinal cord compression not definitively treated with surgery and/or radiation, or previously diagnosed and treated spinal cord compression without evidence that disease has been clinically stable for > 2 weeks prior to randomization
- Known CNS disease, except for treated asymptomatic CNS metastases, provided all of the following criteria are met: measurable disease outside the CNS, only supratentorial and cerebellar metastases are allowed (i.e., no metastases to midbrain, pons, medulla, or spinal cord), no evidence of progression or hemorrhage after completion of CNS-directed therapy, no ongoing requirement for dexamethasone as therapy for CNS disease (anticonvulsants at a stable dose are allowed), no stereotactic radiation within 7 days or whole-brain radiation within 14 days prior to randomization.
- Leptomeningeal disease
- Uncontrolled tumor-related pain: patients requiring narcotic pain medication must be on a stable regimen at registration. Symptomatic lesions (e.g., bone metastases or metastases causing nerve impingement) amenable to palliative radiotherapy should be treated prior to randomization. Patients should be recovered from the effects of radiation. There is no required minimum recovery period. Asymptomatic metastatic lesions whose further growth would likely cause functional deficits or intractable pain (e.g., epidural metastasis that is not presently associated with spinal cord compression) should be considered for loco-regional therapy if appropriate prior to randomization.
- Uncontrolled hypercalcemia (> 1.5 mmol/L ionized calcium or calcium > 12 mg/dL or corrected serum calcium > ULN) or symptomatic hypercalcemia requiring continued use of bisphosphonate therapy. Patients who are receiving denosumab must discontinue denosumab use and replace it with a bisphosphonate instead while on study. Patients receiving a bisphosphonate for skeletal metastases are not excluded and can continue treatment.
- Malignancies other than TNBC within 5 years prior to randomization, with the exception of those with a negligible risk of metastasis or death and treated with expected curative outcome (such as adequately treated carcinoma in situ of the cervix or basal or squamous cell skin cancer).
- Concurrent anti-cancer therapy (chemotherapy, radiation therapy, surgery, immunotherapy, hormonal therapy, biological therapy) other than the ones specified

in the protocol. Any standard or investigational drugs should be discontinued 2 weeks prior to the first dose of study medication.

### *General Medical Exclusion Criteria*

- Women only: pregnancy or lactation
- Evidence of significant uncontrolled concomitant disease that in the opinion of the investigator could affect compliance with the protocol or interpretation of results, including significant liver disease (such as cirrhosis, uncontrolled major seizure disorder, or superior vena cava syndrome)
- Significant cardiovascular disease, such as New York Heart Association (NYHA) cardiac disease (Class II or greater), myocardial infarction within 3 months prior to randomization, unstable arrhythmias, or unstable angina. Patients with a known left ventricular ejection fraction (LVEF) < 40% will be excluded. Patients with known coronary artery disease, congestive heart failure not meeting the above criteria, or LVEF < 50% must be on a stable medical regimen that is optimized in the opinion of the treating physician, in consultation with a cardiologist if appropriate.
- Severe infection requiring systemic treatment within 4 weeks prior to randomization, including but not limited to hospitalization for complications of infection, bacteremia, or severe pneumonia
- Major surgical procedure within 4 weeks prior to randomization or anticipation of the need for a major surgical procedure during the course of the study other than for diagnosis. Placement of central venous access catheter(s) (e.g., port or similar) is not considered a major surgical procedure and is therefore permitted.
- History of severe reactions (e.g. allergic, anaphylactic, or other hypersensitivity) to chimeric or humanized antibodies or fusion proteins
- Known hypersensitivity or allergy to biopharmaceuticals produced in Chinese hamster ovary cells or any component of the atezolizumab formulation
- History of autoimmune disease, including but not limited to myasthenia gravis, myositis, autoimmune hepatitis, systemic lupus erythematosus, rheumatoid arthritis, inflammatory bowel disease, vascular thrombosis associated with antiphospholipid syndrome, Wegener's granulomatosis, Sjögren's syndrome, Guillain-Barré syndrome, multiple sclerosis, vasculitis, or glomerulonephritis. Patients with a history of autoimmune-related hypothyroidism on a stable dose of thyroid replacement hormone are eligible for this study. Patients with controlled Type 1 diabetes mellitus on a stable insulin regimen are eligible for this study.

- Prior allogeneic stem cell or solid organ transplantation
- History of idiopathic pulmonary fibrosis (including pneumonitis), drug-induced pneumonitis, organizing pneumonia (i.e., bronchiolitis obliterans, cryptogenic organizing pneumonia), or evidence of active pneumonitis on screening chest CT scan. History of radiation pneumonitis in the radiation field (fibrosis) is permitted.
- Positive test for HIV (testing required prior to registration)
- Active hepatitis B (defined as having a positive hepatitis B surface antigen [HBsAg] test at screening) or hepatitis C
- Patients with past hepatitis B virus (HBV) infection or resolved HBV infection (defined as having a negative HBsAg test and a positive antibody to hepatitis B core antigen [anti-HBc] antibody test) are eligible.
- Patients positive for hepatitis C virus (HCV) antibody are eligible only if polymerase chain reaction (PCR) is negative for HCV RNA.
- Active tuberculosis
- Receipt of a live, attenuated vaccine within 4 weeks prior to initiation of study drug (C1D1) or anticipation that such a live, attenuated vaccine will be required during the study
- Prior treatment with CD137 agonists, anti-PD-1, or anti-PD-L1 therapeutic antibody or pathway-targeting agents
- Treatment with systemic immunostimulatory agents (including but not limited to interferons or IL-2) within 4 weeks or five half-lives of the drug (whichever is shorter) prior to randomization
- Treatment with systemic corticosteroids or other systemic immunosuppressive medications (including but not limited to prednisone, dexamethasone, cyclophosphamide, azathioprine, methotrexate, thalidomide, and anti-tumor necrosis factor [TNF] agents) within 2 weeks prior to cycle 1, day 1, or anticipated requirement for systemic immunosuppressive medications during the trial. Patients who have received acute, low-dose, systemic immunosuppressant medications (e.g., a one-time dose of dexamethasone for nausea) may be enrolled in the study. Patients on a stable low dose ( $\leq 10$  mg) daily prednisone or equivalent are allowed on study. Patients with a history of allergic reaction to IV contrast requiring steroid pre-treatment should have baseline and subsequent tumor assessments performed using MRI. The use of inhaled corticosteroids for chronic obstructive pulmonary disease, mineralocorticoids (e.g., fludrocortisone) for patients with orthostatic hypotension, and low-dose supplemental corticosteroids for adrenocortical insufficiency are

allowed.

- Psychiatric illness/social situations that would compromise patient safety or limit compliance with study requirements

### 5.3 Inclusion of Underrepresented Populations

Individuals of all races and ethnic groups are eligible for this trial. There is no bias towards age or race in the clinical trial outlined. This trial is open to the accrual of men and women.

## 6. REGISTRATION PROCEDURES

All patients **MUST** be registered with the Vanderbilt-Ingram Cancer Center (VICC) prior to the start of protocol treatment. Each participating site must also be registered with their own institution according to their institutional guidelines prior to start of protocol treatment.

### 6.1 Guidelines for all participating institutions

Prior to registration, a copy of the IRB approval at the site will be requested and kept on file at the Vanderbilt-Ingram Cancer Center (VICC) Coordinating Center. Eligible participants will be entered on study centrally at the [REDACTED] to verify slot availability prior to enrollment.

**All patients MUST be registered with the VICC prior to the start of protocol treatment. Registration can only be conducted during the business hours of 8AM – 5PM Central Standard Time Monday through Friday.**

- 1) All sites must email the VICC CTSR Coordinating Center at [REDACTED] to notify of upcoming registration and ensure slot availability. The following information should be included in your email:
  - Study number
  - Patient initials
  - Disease type
  - Anticipated consent date
  - Anticipated start date
- 2) To request a subject ID number, the site must submit the following documents with their email notification to the Coordinating Center:
  - Copy of the patient's signed and dated Informed Consent including documentation of the consent process.
  - HIPAA authorization form (if separate from the main consent form)

- VICC Patient Enrollment Form

The Coordinating Center will then provide a subject ID number via email.

- 3) Once the patient has been deemed eligible by the site, an email with the following documents must be sent to the Coordinating Center for eligibility review and patient enrollment [REDACTED]:
- Copy of the patient's signed and dated Informed Consent, including documentation of the consent process.
  - HIPAA authorization form (if separate from the main consent form)
  - VICC Patient Enrollment Form
  - Eligibility supporting documents such as pathology reports, laboratory tests, etc. *or* EMR access. Note: all source documents should be de-identified and screening/subject ID number added prior to sending.
  - Tissue Block Registration Form (see the **Lab Manual**)
  - Signed and completed Eligibility Checklist. **To be eligible for registration to the study, the participant must meet each inclusion and exclusion criterion listed in the eligibility checklist.**

**Note:** All study documents should be received 24-48 hours prior to the patient's anticipated start date. Same day treatment registrations will only be accepted with prior notice and discussion with the Coordinating Center. Please email the Coordinating Center if enrollment is needed sooner.

Upon satisfactory review of eligibility documents submitted, the Coordinating Center will approve enrollment and issue a subject ID number if one was not issued at screening. Once registration/enrollment confirmation from Coordinating Center is received, the site may proceed with protocol procedures.

Please contact the assigned Study Contact with any questions regarding this process. You can also reach out to your assigned CRA once the study is activated.

The VICC Coordinating Center will assign sequence numbers to all patients in screening. Only patients deemed eligible will be randomized to a treatment arm. Sequence numbers will only be re-used if a patient screen fails and then re-screens. The Coordinating Center will randomize eligible patients to carboplatin + atezolizumab or carboplatin alone. Following registration and randomization, eligible participants should begin protocol treatment within 1 week. Issues that would cause treatment delays should be discussed with the Protocol Chair. If a participant does not receive protocol therapy following randomization within allowed time period, the participant will become ineligible and will not be enrolled on study. Such patients will have to undergo screening again to participate in the study in the future. Any requests for eligibility exceptions and/or deviations must be approved in writing by the Protocol Chair, as well as any committees required by local

institutional policies. As is generally accepted, standard of care procedures performed prior to consent, but within the protocol defined screening window for each assessment can be used for study purposes. All research only procedures must be performed after the consent date.

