## 8. TREATMENT PLAN

### 8.1 Overview

This is an open-label phase II multi-institution trial that evaluates the safety profile and anti-tumor activity of carboplatin +/- atezolizumab in patients with metastatic triple negative (ER negative, PR negative, HER2neu negative by IHC or FISH) breast cancer. Patients will be treated with carboplatin AUC 6 IV on day 1 and atezolizumab 1200 mg IV on day 1 of a 21 day cycle or carboplatin AUC 6 IV on day 1 of a 21 day cycle. For patients on the combination arm, atezolizumab is to be administered prior to carboplatin. For patients on the combination arm, carboplatin can be stopped after cycle 6 and atezolizumab can be continued as a single-agent at the discretion of the treating physician.

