### **8.7 Criteria for Removal from Study**

Patients will be removed from study when any of the criteria listed below apply. All patients who initiate protocol treatment will be included in the overall evaluation of response (intent-to-treat analysis). All reasons for discontinuation of therapy should be documented clearly in the medical record.

If a subject discontinues or withdraws from the study, every reasonable attempt will be made to get a tissue/tumor biopsy, along with blood, at the end of treatment, if the subject is able and willing.

Patients may be withdrawn from the study if they experience any of the following:

- Disease progression, per investigator assessment by RECIST (or irRECIST for atezolizumab arm)
- Intolerable toxicity to atezolizumab or carboplatin. Patients assigned to carboplatin + atezolizumab who experience toxicity to atezolizumab or carboplatin can continue on study with single agent carboplatin or atezolizumab, respectively, at the discretion of the treating physician. Patients will be followed for disease progression and should continue radiologic assessments every 3 cycles as per the study.

Other reasons for patient discontinuation may include, but are not limited to, the following:

- Non-compliance with the study protocol, including, but not limited to not attending the majority of scheduled visits. The Protocol Chair will determine when non-compliance should lead to removal from study. Note: The patients will still be included in the overall evaluation of response (intent-to-treat analysis).
- Patient personal decision. The reason for discontinuation from the study must be documented. The patients will be included in the overall evaluation of response (intent-to-treat analysis) if any protocol therapy was administered prior to withdrawal.
- If the patient becomes pregnant
- Patient is lost to follow-up
- Study is terminated for any reason

The investigator has the right to discontinue a patient from the study for any medical condition that the investigator determines may jeopardize the patient's safety if he or she continues in the study; for reasons of noncompliance (e.g., missed doses, visits); or if the investigator determines it is in the best interest of the patient. The Protocol Chair should be notified in such cases.

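### Section 6.1 removes a randomised patient who does not start treatment in time, and the plan never says whether the primary PFS analysis keeps that patient

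*Combined protocol and SAP*

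**What the plan says.** Section 6.1 has the Coordinating Center randomise only patients already found eligible, and asks that treatment begin within 1 week of registration and randomisation. It continues: "If a participant does not receive protocol therapy following randomization within allowed time period, the participant will become ineligible and will not be enrolled". On re-entry it adds: "Such patients will have to undergo screening again to participate in the study in the future". On identifiers it says: "Sequence numbers will only be re-used if a patient screen fails and then re-screens". It does not say whether a randomised non-starter counts as a screen failure, or whether the first allocation stands on return.

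Section 8.1 gives the masking: "This is an open-label phase II multi-institution trial".

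The texts that could define a population are these:

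- **Sections 3.1, 12, 17.1 and 17.2** give the PFS objective, the RECIST rule, the Kaplan-Meier estimate and the log-rank sample size. None names an analysis set. Section 17.4, headed as the statistical analysis plan, defines none either.
- **Section 8.7**: "All patients who initiate protocol treatment will be included in the overall evaluation of response (intent-to-treat analysis". A patient who withdraws by personal decision is kept only if some protocol therapy was given. Both statements concern response.
- **Section 12.1** defines sets for toxicity and objective response only.
- **Section 17.5** requires every patient included in the study, even an ineligible one, to be assessed for safety, tolerability and response. It does not mention PFS.
- **Section 8.6** counts yearly chart review for progression from the last dose of study drug, so it schedules none for a patient who was never dosed.

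**The concern.** Removal here comes after allocation, when the arm can be known. A comparison of randomised arms is protected because nothing after allocation decides who is counted. If patients who decline or delay one arm differ in prognosis from those who stay, the remaining arms no longer match, and the log-rank test does not hold its one-sided 0.10 level. Losing good-prognosis controls favours the combination. Losing poor-prognosis controls works against it.

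There are two further risks. With no stated PFS set, an analyst could defend including or excluding non-starters after seeing the data. And if a returning patient were randomised again, the same person could hold two allocations.

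**Working it through.** **1. The plan's own figure.** Inputs from Section 17.2: medians 2.9 and 4.4 months, one-sided alpha 0.10, power 80%, accrual 24 months, further follow-up 12 months, 1:1 allocation.

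- Exponential hazard ratio: 2.9/4.4 = 0.659.
- Events (Schoenfeld): 4(1.2816 + 0.8416)² / (ln 0.659)² = 104 after rounding up.
- Event probability: 1 − (e^(−12λ) − e^(−36λ))/(24λ), with λ = ln 2/median. This gives 0.990 for control and 0.961 for the combination, mean 0.976.
- Total: 104/0.976 ≈ 106.6, against 106 stated. Power at 106 patients is 0.799.

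The sample size reproduces. Its stated assumptions contain no allowance for non-starters.

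**2. Loss of power from exclusion is minor.** Removing 5 of 106 leaves 101 × 0.976 ≈ 98.5 events and power 0.785.

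**3. Effect on type I error.** This was a log-rank simulation with no treatment effect: 53 randomised per arm, control median 2.9 months, and accrual and follow-up as above. Both arms contain the same fraction of decliner-type patients, whose hazard relative to the others is varied. All control decliners are removed. Combination decliners are removed never, half the time or always. The fractions and relative hazards are assumptions, because the documents give neither. There were 100,000 runs per case (standard error about 0.001). With no loss the simulated error is 0.101 to 0.105.

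| Who is lost | Fraction (of 53) | Hazard 0.5 | 0.7 | 1.0 | 1.5 |
|---|---|---|---|---|---|
| Control only | 2% (about 1) | 0.120 | 0.111 | 0.103 | 0.097 |
| Control only | 5% (about 3) | 0.145 | 0.122 | 0.104 | 0.090 |
| Control only | 10% (about 5) | 0.192 | 0.141 | 0.104 | 0.077 |
| Combination loses half as many | 2% | 0.111 | 0.108 | 0.102 | 0.100 |
| Combination loses half as many | 5% | 0.124 | 0.111 | 0.104 | 0.094 |
| Combination loses half as many | 10% | 0.144 | 0.122 | 0.103 | 0.089 |

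Equal loss in both arms gives 0.101 to 0.104 throughout. So does keeping every randomised patient with complete outcomes (0.100 to 0.104).

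**4. What the fix achieves when outcomes are missing.** A patient censored at randomisation adds nothing to a log-rank test, so the result equals exclusion. Suppose outcomes are retrieved for half of the non-starting controls (an assumption), with control-only loss and relative hazard 0.5. A separate run of 40,000 per case gives 0.109, 0.121 and 0.142 at 2%, 5% and 10% non-starting. Exclusion in that run gives 0.117, 0.145 and 0.194. About half the inflation remains.

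**The case against.** **Few patients are likely to be affected.** Section 6.1 works close to the start date: "All study documents should be received 24-48 hours prior to" the planned start, and "Same day treatment registrations will only be accepted with prior notice and discussion with the Coordinating Center". Delays go to the Protocol Chair, and "Any requests for eligibility exceptions and/or deviations must be approved in writing by the Protocol Chair". Section 8.4 lets control patients cross over at progression, which weakens the motive to decline that arm. At 2% the error stays between 0.097 and 0.120. The value 0.192 needs 10% loss from one arm only and a halved hazard. All of this stands and limits the size of the point. It does not supply the missing analysis set.

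**Section 17.5 keeps ineligible patients.** That is general inclusion language, and it pulls against exclusion. But it covers safety, tolerability and response only. Whether someone whom Section 6.1 treats as never enrolled is still included in the study is exactly what remains open.

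**The remedy is imperfect.** Yearly chart review is not comparable with scans every 9 weeks when the assumed medians are 2.9 and 4.4 months. Consent for follow-up of patients recorded as not enrolled cannot be judged from these documents. Both objections stand and are reflected in the fix.

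**Stronger readings.** A reader might infer that the plan does exclude non-starters from PFS. The exploratory body-composition analysis in Section 17.3, which describes 53 patients as receiving atezolizumab, may seem to confirm it. That number is simply the planned arm size, and no text states the exclusion. A reader might also infer that returning patients are randomised afresh. Section 6.1 is silent on that.

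**Conclusion.** The gap is real and lies in the primary comparison. Section 6.1 removes patients after randomisation in an open-label trial, no section defines the PFS set, and the nearest texts (Sections 6.1, 8.6 and 8.7) lean towards exclusion, with Section 17.5 pulling partly the other way. How a re-screened patient's first allocation is treated is also unstated.

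Under assumed control-only loss and relative hazards from 0.5 to 1.5, the one-sided error is about 0.10 to 0.12 at 2% and 0.09 to 0.145 at 5%, against a nominal 0.10. It can fall as well as rise, and it is not inflated if loss is equal in both arms. The documents do not show that non-starting was differential, common or related to prognosis, so they do not support saying that the trial's result is biased. The plan should be corrected, but the likely size is modest.

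**What to change.** - **Section 17:** define the primary PFS set and the OS set as all randomised patients by first assigned arm, timed from randomisation. Give a treated-only PFS analysis as a sensitivity analysis.
- **Section 6.1:** link a re-screened patient's registrations and keep the first allocation for analysis.
- **Section 8.6:** follow never-treated patients for progression and survival from randomisation as far as consent allows, using scan dates from usual care where available. State how off-study therapy before progression is handled.
- **Reporting:** give non-starters by arm, with reasons. State that the error rate is protected only to the extent that their outcomes are obtained, and add a sensitivity analysis for non-starters without data.

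When a late patient may be dosed or must be re-screened is for the sponsor to reconcile. The response and clinical benefit populations are a separate matter.

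**Cost.** The prospective wording is cheap. The cost of retrieving outcomes for patients already recorded as not enrolled is unknown.

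Power falls slightly. Simulated power is 0.79 with no decliners. With all randomised patients kept, at 2% to 10% decliners, it is 0.77 to 0.79 if only controls fail to start, and 0.73 to 0.79 if half as many combination patients also do. Both ranges assume that non-starters get no comparable benefit elsewhere. In the extreme case where every non-starting control obtains the full combination effect off study, power is 0.75 to 0.78 at 2%, 0.70 to 0.76 at 5% and 0.61 to 0.74 at 10%.

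### Section 6.1 lets a randomised non-starter return through screening without saying the first allocation stands, so the text permits a second draw after the arm is known

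*Combined protocol and SAP*

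**What the plan says.** Allocation is central and follows eligibility review. Section 6.1 states "Only patients deemed eligible will be randomized to a treatment arm" and "The Coordinating Center will randomize eligible patients to carboplatin + atezolizumab or carboplatin alone". On timing it says "Following registration and randomization, eligible participants should begin protocol treatment within 1 week", and on delays "Issues that would cause treatment delays should be discussed with the Protocol Chair".

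For a randomised patient who is not treated in the allowed time, the same section says "the participant will become ineligible and will not be enrolled on study", and then "Such patients will have to undergo screening again to participate in the study in the future".

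On numbering, Section 6.1 says "Sequence numbers will only be re-used if a patient screen fails and then re-screens". It does not say which number a patient receives who was randomised, did not start, and later returns.

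Section 8.1 fixes the blinding: "This is an open-label phase II multi-institution trial". Section 8.7 labels its evaluation of response as intent-to-treat but builds it from patients who began protocol treatment. For those who leave by personal decision, it requires that some protocol therapy was given first. Section 17 names no separate analysis population for PFS.

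**The concern.** Randomisation protects the comparison only if each patient is allocated once, before anyone knows the result. Here the arm can be known up to a week before treatment, failing to start removes the patient from the study, and the protocol provides a way back in. A patient or site disappointed by carboplatin alone could let the window lapse and be allocated again.

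Such movement would run in one direction and by choice. Patients able to wait for a second screening may be fitter or slower to progress than the rest. That is plausible, though the documents offer no evidence for it. If it is so, the redraw shifts better-prognosis patients from control to combination and the primary PFS comparison favours the combination without any drug effect. A set limited to treated patients would not show this, because the first allocation never appears in it.

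**Working it through.** **1. What the text permits.** Put in order, the rules are:
- the arm is allocated centrally and is not blinded (6.1, 8.1);
- the patient should start within 1 week (6.1);
- a non-starter becomes ineligible and is not enrolled (6.1);
- the non-starter may take part later after a new screening (6.1);
- the only described way onto an arm is randomisation of eligible patients (6.1);
- no section retains the first arm, bars a second allocation, or requires a check for an earlier one.

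A site following these rules literally can obtain a second draw. Under 8.7, only the allocation that led to treatment is counted.

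**2. The plan's own sample size (17.2).** Inputs: medians 2.9 and 4.4 months, one-sided alpha 0.10, 80% power, 24 months of accrual, 12 months of further follow-up, 1:1 allocation.
- Hazard ratio with exponential PFS: 2.9/4.4 = 0.659.
- Events (Schoenfeld): 4 × (1.2816 + 0.8416)² / (ln 0.659)² = 104, rounded up.
- Probability of an event with λ = ln 2/median: 1 − [exp(−12λ) − exp(−36λ)]/(24λ), which gives 0.990 (control) and 0.961 (combination).
- Patients: 104/0.9755 = 106.6, against the stated 106. Expected events from 106 patients: 53 × (0.990 + 0.961) = 103.4, giving 79.9% power.

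The stated design reproduces, and nothing in this point disputes it.

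**3. How many patients would move.** One redraw raises the chance of the combination from 0.5 to 0.5 + 0.5 × 0.5 = 0.75. Let f be the assumed share of patients who would redraw once if given control. Of 53 control allocations, 53f are redrawn and half of those change arm.

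| f | Redrawn | Moved to combination | Final combination share (0.5 + 0.25f) |
|---|---|---|---|
| 2% | 1.1 | 0.5 | 50.5% |
| 5% | 2.7 | 1.3 | 51.3% |
| 10% | 5.3 | 2.7 | 52.5% |
| 20% | 10.6 | 5.3 | 55.0% |

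Power under this imbalance alone stays at 79.6% to 79.9%. The possible harm is selection bias, not lost power.

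**4. Effect on the type I error.** Simulation with no treatment effect: 106 patients, exponential PFS with median 2.9 months, 24 + 12 months, log-rank test rejecting at z < −1.2816. Every would-be redrawer given control redraws once, and redrawers have relative hazard r. The delay between draws is not modelled. With 6,000 trials per cell the Monte Carlo standard error near 0.10 is √(0.1 × 0.9/6000) = 0.004. Ranges below span independent runs.

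| f | r = 0.7 | r = 0.5 |
|---|---|---|
| 2% | 0.11 | 0.11–0.12 |
| 5% | 0.12–0.13 | 0.14–0.15 |
| 10% | 0.13–0.14 | 0.18–0.19 |
| 20% | 0.17 | 0.25–0.26 |

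With r = 1 the rate is 0.10 to 0.11 at every share. A milder prognostic difference (f = 5%, r = 0.85) gives 0.112.

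**5. Effect of the remedies.** Grouping the same patients by first allocation at r = 0.5 returns the rate to about 0.10 (0.103 at f = 10%, 0.102 at f = 20%). Keeping patients in their first arm has the same effect in this model.

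**The case against.** The strongest reply is that the protocol never says such patients are randomised again. It says they are screened again, and the sentence about eligible patients limits who may be randomised without ordering a fresh draw. This stands: the second draw is an inference. It remains the only way the written procedure gives a returning patient an arm, so the text permits it without commanding it.

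A reader might go further and infer that the patient gets a new number and that the two allocations cannot be linked. The documents do not show that. A non-starter who becomes ineligible could be handled as a screen failure, in which case the sequence number is re-used. Even with a new number, one Coordinating Center holds the consent, initials and enrolment form and performs the randomisation, so it has the means to recognise the patient. What is missing is an instruction to check.

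A reader might also infer that no analysis could repair a redraw because the patient holds two allocations. Step 5 shows otherwise for the type I error.

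Several features make redraws less likely. Central randomisation means a site cannot redraw by itself. Delays should be raised with the Protocol Chair. Control patients may cross over to atezolizumab at progression (8.4), so a control allocation does not close off the drug. Waiting also postpones treatment in a disease with an assumed control median PFS of 2.9 months, for an even chance of the same arm. These points reduce the likely frequency, but none forbids a second draw. Crossover comes only at progression, after the PFS event has occurred.

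**Conclusion.** The point holds as a permission that the text leaves open: a second allocation is possible after the first is known, and under 8.7 the first would disappear from the analysis set. The documents do not show that redraws are ordered, frequent or untraceable.

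The size is conditional. For shares of 2% to 20% and relative hazards of 0.5 to 0.7, the nominal one-sided 0.10 becomes about 0.11 to 0.26. At 2% the inflation is slight, and without a prognostic difference there is essentially none. The share, the assumption that every such control patient redraws, and the prognostic difference are all assumptions. The step from 8.7 to PFS also assumes that the treated-only set applies to the primary endpoint, since Section 17 names no other.

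This is a cheap improvement to the protection of the primary comparison. No change to the sample size follows.

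**What to change.** In Section 6.1, state that each patient is randomised once, that a returning patient who was already randomised keeps the original sequence number and arm, and that the Coordinating Center checks for a prior allocation before randomising.

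In Section 17, state that any patient who nevertheless received two allocations is analysed by the first, with PFS counted from first randomisation. This is the backstop. Keeping the original arm is preferable, because a patient analysed as control but treated with the combination would dilute a true effect.

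The cost is a sentence or two in each section and a duplicate check within the existing central registration. The downside is that a few patients who would return only for a new draw may not come back.
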